7. DURATION OF FOLLOW-UP

Study participation involves 2 study visits for breast screening – one at the beginning of the study and a second visit one year later. Participants will be enrolled in the study for approximately 2.5 years (30 months) to ascertain breast cancer status, and may be contacted at the end of study if breast cancer status cannot be ascertained based on chart review, alone. If only one of the baseline

imaging tests (DBT or MBI) is completed, the patient will be excluded from the study and no data will be collected. Participant's breast cancer status will be obtained from chart review or patient contact targeted for 365 days after each screening year, but may be obtained from 335 days to 455 days after screening, unless the patient specifically requests to withdraw from the study. If a patient is diagnosed with a primary breast cancer during the study period, no subsequent follow-up or further study imaging will be required for this research study.

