8.1.3 Participants Not Meeting Reference Standard Definitions

If a participant does not meet either definition for Positive or Negative Breast Cancer Status in a given screening year, for instance a participant who has no known breast cancer diagnosis but has no information available via chart review and cannot be contacted, will be considered “lost to follow up” and assumed to not have breast cancer in the analysis. In the event of a participant’s death, the date of death and cause of death will be recorded to determine if breast cancer was diagnosed and the length of follow up.

^aThe date of histopathologic breast cancer diagnosis is defined as the date on which tissue was obtained via biopsy or surgical excision, and subsequently determined to include invasive cancer (with or without DCIS) or DCIS.

^bYear 1 screening is defined as having both Year 1 MBI and Year 1 DBT. If not performed on the same day, the date of Year 1 screening is the day Year 1 MBI is performed.

^cYear 2 screening is targeted to be performed with both MBI and DBT approximately 365 days (target range 335 – 455 days) after Year 1 screening MBI. For purposes of establishing breast cancer status of Screening Year 1, Year 2 screening may be performed with any combination of breast imaging tests, most often including MBI, DBT, or both, but may also include breast MRI, WBUS, or CEDM; testing may be performed for either screening or diagnostic indications. The date of Year 2 screening used for reference standard is the earliest of these tests performed at least 335 days after Y0 screening.

^dYear 2 screening is not conducted as part of the research study, but considered for purposes of establishing Year 2 breast cancer status as any documentation of breast imaging (MBI, DBT, MRI, WBUS, or CEDM) performed within 335 – 455 days after Year 2 screening.

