8.4 Definition of Analysis Set

The Analysis Set for each screening year will be defined as the subset of enrolled patients who met eligibility criteria and completed screening imaging with both DBT and MBI.

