5. To assess the rate of interval cancers with incorporation of MBI screening.

For the purpose of our analysis, interval cancers are defined as cancers diagnosed not at study imaging but between Year 1 and Year 2 screening tests. The interval cancer rates per 1000 women screened will be determined as the proportion of participants in the analysis set who had an interval cancer diagnosed and verified by pathology. To assess whether the incorporation of MBI screening, with one year of follow-up for breast cancer results in a “low” interval cancer rate, we will compare the interval cancer rate found in our study to the reported interval cancer rates for a population of women with dense breasts.

Per Breast Cancer Surveillance Consortium (BCSC) analysis³⁸ the interval cancer rate among women with dense breasts was 89 per 100,000 women (or ~0.9 per 1000). The authors of this analysis considered an interval cancer rate greater than 1 case per 1000 mammography examination as an unacceptable performance level. We will estimate the rate of interval

cancers from our study and provide a 95% confidence interval. The performance level of this screening approach will be considered unacceptable if the lower bound of the confidence interval exceeds 1/1000 (i.e. 7 or more interval cancers in this cohort).

6. To examine the relative performance of DBT and MBI within subgroups categorized by breast cancer risk.

The comprehensive risk factor collection planned in this study will allow accurate risk estimation promoting generalizability of results by type of risk model and level of risk. As an exploratory analysis, we will examine if the risk estimates determined with Gail, BCSC, Claus, and Tyrer-Cuzick models may predict a subgroup of women with MDB who are more likely to benefit from a specific supplemental screening. In particular, the relative performance of the screening modalities (sensitivity and specificity) will be characterized separately, within subgroups of patients defined by various levels of risk. The statistical power to discern differential performances of the screening modalities among different risk subgroups may be limited due to the restricted sample size in these subgroup analyses.

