8.8 Considerations for Expected Attrition

To account for attrition due to incomplete follow-up leading to non-evaluability of the primary endpoints or inconclusive findings from either screening modality, we will plan to over accrue an additional 375 participants, which leads to a **total sample size of N = 3006**. A high rate of missing data is not anticipated. For baseline variables that have more than 10% data missing, the missingness pattern will be examined and when appropriate, missing data imputation techniques may be employed.

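### The fixed count of 7 interval cancers matches an exact 95% lower bound above 1/1000 only up to 2815 women, while the analysis set can reach 3006; women of unknown status count as cancer-free with no sensitivity analysis

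*Combined protocol and SAP*

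**What the plan says.** Section 8.6, item 5, defines the interval cancer rate as a proportion "determined as the proportion of participants in the analysis set who had an interval cancer diagnosed and verified by pathology". It promises a 95% confidence interval, says "we will compare the interval cancer rate found in our study to the reported interval cancer rates", and sets one decision rule: performance is unacceptable if the "lower bound of the confidence interval exceeds 1/1000 (i.e. 7 or more interval cancers in this cohort". The interval method and the N behind the 7 are not given.

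Section 8.4 limits the analysis set to eligible women who "completed screening imaging with both DBT and MBI". Follow-up is not a condition. Section 8.1.3 keeps women with no diagnosis and no obtainable information, who are "assumed to not have breast cancer in the analysis". Section 7 removes a woman with only one baseline exam: "the patient will be excluded from the study and no data will be collected".

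Section 8.7 requires 2631 women. Section 8.8 adds 375, giving 3006, to cover "attrition due to incomplete follow-up leading to non-evaluability of the primary endpoints or inconclusive findings from either screening modality". Its missing-data provision concerns baseline variables only. No sensitivity analysis for unknown cancer status appears.

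**The concern.** The rule is written twice, as a bound and as a count, and the two are equivalent only over a range of N. If the final denominator lies outside that range, the same data can be called unacceptable by one half of the sentence and not by the other. The choice would then be made after the data are seen.

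The handling of unknown status matters for the same endpoint. Treating a woman who cannot be traced as cancer-free can only remove interval cancers from the numerator while leaving her in the denominator. It therefore lowers the interval rate and raises NPV, both in favour of the screening approach under study.

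**Working it through.** **Inputs.** Threshold 1/1000 and count 7 (Section 8.6, item 5); powered N 2631 (8.7); enrolment 3006 (4 and 8.8); denominator is the analysis set (8.4, 8.6). Assumption: two-sided exact (Clopper-Pearson) 95% interval. The plan does not name it here, but uses an exact binomial test for the primary endpoint (8.5, 8.7) and exact binomial distributions for advanced cancers (8.6, item 4).

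**Formula.** The lower limit for x cancers in N women is the 0.025 quantile of Beta(x, N − x + 1). It exceeds 0.001 exactly when P(X ≥ x | N, 0.001) < 0.025.

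**The plan's own figure.** At N = 2631, 7 cancers give a lower limit of 1.07 per 1000, with P(X ≥ 7 | 0.001) = 0.0181, and 7 is the smallest count that qualifies. The stated count reproduces.

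**Other N, exact interval.**

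| N | Cancers | Lower limit per 1000 | P(X ≥ x) at 1/1000 |
|---|---|---|---|
| 2815 | 7 | 1.0003 | 0.02496 |
| 2816 | 7 | 0.99998 | 0.02500 (just above 0.025) |
| 3006 | 7 | 0.94 | 0.0337 |
| 3006 | 8 | 1.15 | 0.0120 |

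The cut-off is 7 for N = 2204 to 2815 and 8 for N = 2816 to 3006.

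**Can N exceed 2815?** With 3006 enrolled, N falls to 2815 only if 3006 − 2815 = 191 women (191/3006 = 6.4%) are ineligible, withdraw or lack a Year 1 exam. Loss to follow-up after both exams does not count towards the 191, because 8.1.3 keeps those women in.

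**Consequence at N = 3006.** Chance of an unacceptable verdict:

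| True rate | Count of 7 or more | Exact bound (8 or more) | Exactly 7 |
|---|---|---|---|
| 1/1000 | 3.4% | 1.2% | 3.4 − 1.2 = 2.2% |
| 2/1000 | 39.6% | 25.8% | 39.6 − 25.8 = 13.8% |

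At a true 1/1000 the fixed count flags 3.4%, against the 2.5% at most that an exact two-sided 95% lower limit allows.

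**Other interval methods at N = 3006.** Wilson (with or without continuity correction), Agresti-Coull, Jeffreys and mid-p give 7; exact Poisson gives 8; Wald gives 9. At N = 2631, Wilson gives 6.

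**Unknown status.** The plan gives no loss rate, so these figures are illustrations. Take a true rate of 2 per 1000, N = 3006, and L women lost. L = 375 is a ceiling, being the whole reserve.

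- If lost women contribute no diagnoses, the plan's rule reads 2 × (3006 − L)/3006: 1.90 for L = 150 and 1.75 for L = 375.
- If loss is even over the year and earlier diagnoses are known, cases are 0.002 × (3006 − L/2): 5.862 (L = 150) or 5.637 (L = 375).
  - Divided by 3006 (the plan's rule): 1.95 or 1.88.
  - Divided by the 2856 or 2631 ascertained women: 2.05 or 2.14.
  - Divided by 3006 − L/2 = 2931 or 2818.5 woman-years: 2.00 in both.

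Restricting to ascertained women overshoots because Section 8.1.2 lets a diagnosis count at any time, whereas negative status needs at least 335 days.

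**The case against.** A reader might infer that 7 is an arithmetic mistake. It is not: at the powered N it is the exact cut-off, and reading the cohort as those 2631 women is natural. Nor does the plan commit to Clopper-Pearson here; under Wilson, Agresti-Coull or Jeffreys, 7 still holds at 3006. The final N is unknown too. Ineligibility, single-exam exclusions, withdrawals and women who stop MBI after infiltration (5.1.2) could together reach 6.4%, about half of the 12.5% allowance (375/3006). The count is introduced as a gloss, so an analyst would probably apply the bound. All of this stands. It makes the conflict conditional, and shows that the underlying gap is an unnamed method and N.

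A reader might also infer that staying below the bound is meant to prove a low or acceptable rate. The text never says so; it promises an estimate, an interval and a comparison with published rates. It is enough to note that not crossing the bound does not show a low rate. A true 2/1000 is flagged only 28% of the time at N = 2631 (exact cut-off 7) and 26% at 3006 (cut-off 8).

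On unknown status, the rule is stated openly, 8.1.2 offers several routes to negative status including chart review alone, and 8.8 does not expect much missing data. That limits the bias but does not change its direction.

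**Conclusion.** The point holds in a limited form. Given an exact 95% interval and an analysis set of 2816 to 3006, the written count and the written bound give opposite verdicts when exactly 7 interval cancers occur. At N = 3006 that has probability 2% at a true 1/1000 and 14% at 2/1000. The exact method is inferred from its use elsewhere in the plan.

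The unknown-status rule biases the interval rate downward and NPV upward. At a true 2.00 per 1000 the illustrated readings are 1.75 to 1.95, under assumed losses the plan does not supply. It will seldom change the verdict.

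This is a minor matter on a secondary endpoint. The primary comparison does not use this cut-off and is unaffected.

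**What to change.** In Section 8.6, item 5, name the exact (Clopper-Pearson) interval, let its lower bound at the actual denominator govern, and drop the fixed count. Alternatively, state 7 for N = 2204 to 2815 and 8 for N = 2816 to 3006.

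The Section 8.1.3 rule can stay as the main analysis. Report how many women were unascertained and add one sensitivity analysis of the interval rate based on follow-up time. Censor each woman at last known status and end her time at Year 2 screening, or at day 365 only if she has no Year 2 screening, as in Section 8.1.2. A day-365 cut for everyone would drop interval cancers that the plan counts. State the assumption that loss is uninformative. Do not simply restrict to ascertained women, for the reason shown above.

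The cost is SAP wording, one extra analysis, and a last-known-status date for every woman. For deaths the plan already records information "to determine if breast cancer was diagnosed and the length of follow up".

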8.5 Primary Endpoint

The primary aim for this study is to compare the rate of detection of invasive cancers between DBT alone vs. the combination of DBT with supplemental MBI at Year 1 screening.

For each modality, the detection rate of invasive cancers will be estimated as the proportion of participants in the analysis set who had an invasive cancer detected by the modality and verified by pathology. Because of the paired design and nature of comparing single modality alone vs combined modality screening results, the null hypothesis of equal detection rates is on the boundary of the support and assumptions of a standard 2-sided McNemar's test are violated. The hypothesis will alternatively consider superiority by a margin using an exact binomial test. The margin will be defined such that the increase in rate of detection must be higher than 1 per 1000 (i.e., 0.1%).

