8.7 Sample size and power analysis

The sample size for this clinical trial was chosen to allow adequate power to detect difference in invasive cancer detection between DBT alone vs. the combination of DBT with supplemental MBI.

This is the first study to directly compare performance of DBT and MBI. Our choice of plausible values for the incremental detection of invasive cancers anticipated for MBI at Year 1 imaging, relative to DBT, is based on a composite analysis of two studies, one comparing MBI to 2D digital mammography, and one comparing 2D digital mammography to DBT:

- In a previous comparison of MBI to 2D digital mammography in average-risk women with dense breasts, the invasive cancer detection rate was 1.9 (95% CI 0.6 to 5.6) for 2D mammography vs. 8.8 (95% CI 5.1 to 14.7) for 2D mammography plus MBI, giving an incremental cancer detection rate (ICDR) for invasive breast cancers of 6.9 per 1000.¹⁰
- In a comparison of 2D digital mammography and DBT in a general population screening program, the invasive cancer detection rate for women with dense breasts was 3.4 (95% CI 1.5 to 5.4) for 2D mammography vs. 4.7 (95% CI, 2.9 to 6.6) for DBT ($p=0.4$), allowing us to estimate that the ICDR of invasive breast cancers for DBT is 1.3 per 1000.³⁹

Thus the expected difference in invasive cancer detection rate between DBT with supplemental MBI and DBT alone is 5.6 ($=6.9 - 1.3$). We conservatively estimated the difference in yield of invasive breast cancers between DBT with supplemental MBI and DBT alone to be approximately 5 per 1000. To allow for potential smaller effect size that may be observed in a multicenter setting,

as has been observed with other modalities, we chose to power the study to detect an effect size of 4 per 1000 additional invasive cancers detected with supplemental MBI.

We will test the hypothesis that DBT with supplemental MBI results in an incremental invasive cancer detection rate of more than 1 per 1000 screenings (0.1%) compared to that of DBT alone. Assuming the difference in invasive cancer detection rates is 0.004, a sample size of 2631 will be needed to achieve 90% power using a one-sided exact binomial test with significance level alpha = 0.025 (calculation based on PASS 15).

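### The exploratory risk-subgroup analysis (section 8.6, item 6) gives only separate estimates within unspecified risk levels, with no estimate of how the DBT–MBI difference changes with risk

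*Combined protocol and SAP*

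**What the plan says.** Item 6 is the last of the secondary endpoints in sections 2.2 and 8.6 of the combined protocol and SAP, and section 8.6 labels it exploratory. It asks whether estimates from the Gail, BCSC, Claus and Tyrer-Cuzick models "may predict a subgroup of women with MDB who are more likely to benefit from a specific supplemental screening". The method is that the sensitivity and specificity of the two tests "will be characterized separately, within subgroups of patients defined by various levels of risk". The item closes with a caution that power to distinguish performance between risk subgroups may be low.

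Item 6 does not give the number of levels, the cut-points, a lead risk model, the screening year, a contrast across levels, or any statement about looking at four models. Item 2 of the same section gives a binomial interval for sensitivity and comparisons between modalities, but nothing across risk levels.

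**The concern.** The question is comparative: does the difference between DBT and MBI change with predicted risk? Separate estimates within each level do not answer it. The reader has to compare them by eye, with no measure of how far they would differ by chance. The caution about power covers the risk of missing a real difference. It does not cover the opposite risk, that levels differ by chance and the difference is read as a subgroup. Using four risk models gives four occasions for that. Cutting continuous scores into levels also discards information when cancers are few.

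Section 1.5 expects the trial's data to inform individual decisions on supplemental screening, so an apparent gradient could be given more weight than it can bear. The exposure is in sensitivity. Specificity rests on many more women: about 2631 − 23 = 2608 without cancer, or roughly 869 in each of three equal levels.

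**Working it through.** **Plan's own figure.** Section 8.7 states: "Assuming the difference in invasive cancer detection rates is 0.004, a sample size of 2631 will be needed to achieve 90% power". The test there is exact binomial, one-sided at 0.025, and the null rate is the section 8.5 margin of 0.001. With N = 2631, the test rejects at 7 or more additional cancers. P(X ≥ 7) is 0.0181 at 0.001 and 0.9001 at 0.004, and 2631 is the first N that reaches 90%. The figure reproduces. The plan gives no cancer count for the risk subgroups.

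**Expected cancers.** Inputs from section 8.7 are "4.7 (95% CI, 2.9 to 6.6) for DBT" (per 1000) and the planned added yield of 4 per 1000. Section 8.8 gives a "total sample size of N = 3006".

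- Rate: 4.7 + 4 = 8.7 per 1000.
- 2631 × 0.0087 = 22.9 cancers; 3006 × 0.0087 = 26.2.
- Per level, if levels are equal: 11.4 to 13.1 with two, 7.6 to 8.7 with three, 5.7 to 6.5 with four, 4.6 to 5.2 with five.

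The equal levels and their number are assumptions.

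**Scale of chance variation.** For two levels of 8 cancers with common sensitivity s, the standard error of the difference is √(2s(1−s)/8). At s = 0.7 this is √(0.42/8) = 0.23. At s = 0.9 it is √(0.18/8) = 0.15. A 20-point gap is therefore less than one standard error at 0.7 and about 1.3 at 0.9. On 8 cancers the 95% interval is 16% to 84% for 4/8 and 47% to 99.7% for 7/8.

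**One test's sensitivity, no true difference.** Simulation: 23 cancers are allotted at random to equal levels, detection is binomial with the same sensitivity in each level, and gap = highest minus lowest observed sensitivity. Chance that the gap is at least 20 points:

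| 23 cancers | s = 0.6 | 0.7 | 0.8 | 0.9 |
|---|---|---|---|---|
| Three levels | 74% | 71% | 64% | 42% |
| Two levels | 35% | 31% | 24% | 12% |

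With two levels and s = 0.5 it is 37%. For DBT, the plan's rates imply s of about 4.7/8.7 = 0.54. With exactly 8 cancers in each of three levels the chance there is 73%.

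**A larger count.** Sensitivity is defined over all women with breast cancer, the reference standard includes DCIS, and item 6 does not restrict the year. The documents give no DCIS or Year 2 yield. If these brought the total to 46 (an assumption), the three-level figure is 52% at s = 0.6 and 37% at s = 0.8.

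**MBI minus DBT.** This is closer to what item 6 asks. With 23 cancers in three levels, and 52% to 72% of cancers assumed to be found by one test only, the difference varies by at least 20 points between some two levels in 84% to 90% of trials. With exactly 8 per level the range is 72% (MBI finds every DBT-detected cancer) to 87%. With 45 cancers and the 52% to 72% discordance it is 69% to 81%.

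**What a formal comparison can do.** Fisher's exact test on 8 versus 8 cancers has a false-positive rate of at most about 2.1%, and power of about 6% for 0.5 versus 0.7 and 3% for 0.7 versus 0.9. For 80% power at two-sided 0.05, about 93 or 62 cancers per level respectively would be needed.

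**The case against.** The plan calls item 6 exploratory, says performance will be described rather than tested, and admits limited power. No alpha, decision rule or claim depends on it, and descriptive subgroup estimates are normal practice for such an item. This stands, and it keeps the point small. A reader might infer that the plan intends to issue guidance on which women should have MBI. The text does not say so.

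A reader might also infer that a 20-point gap will usually appear by chance, with about 8 cancers per level taken as a feature of the plan. The documents do not support that. The plan fixes neither the number of levels nor the year. For one test the chance is well below half with two levels, and below half with three levels at sensitivity 0.90. A larger count lowers it further. The MBI-minus-DBT figures are higher but rest on an assumed overlap between the tests.

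Finally, a trend analysis would have little power. A continuous-score trend test for one test with 23 cancers has about 14% to 18% power for a true 20-point gap between the top and bottom thirds. This also stands. It argues against making statistical significance a condition for reporting, but not against giving the estimate and its interval.

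**Conclusion.** The point holds as a gap in specification. Item 6 asks a comparative question and plans no comparative estimate, and its caution does not cover chance subgroups. The exploratory label lowers the stakes but does not supply the missing quantity.

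The size depends on choices the plan leaves open. For one test with 23 cancers, the chance of a 20-point gap with no true difference runs from 12% (two levels, sensitivity 0.90) to 74% (three levels, 0.6). For MBI minus DBT across three levels it is about 84% to 90% at the assumed discordance, and 72% at the lowest overlap case examined. These figures are for one risk model. Four models raise the chance by an amount that depends on their correlation, which the documents do not give. The primary endpoint is unaffected. This is a cheap improvement, not a flaw in the trial.

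**What to change.** In section 8.6, item 6, for each risk model, add a modality-by-risk estimate with predicted risk as a continuous score:

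- For sensitivity, use a method suited to few cancers (Firth, or exact or permutation), keeping each woman's two results paired.
- For specificity, fit the corresponding model.
- Report each estimate with a 95% confidence interval as the evidence on effect modification.
- Keep the risk-level tables as description.
- State that four models were examined, and label the results hypothesis-generating. Set no significance threshold for reporting.

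It would also help to state the screening year and whether DCIS counts, since both change the number of cancers.

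The cost is SAP wording and a little more analysis on data already being collected. The sensitivity interval will be wide. The estimate shows that uncertainty and so protects against a false subgroup claim, but it does not add power.
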